### 2.3.4 Handling of Missing Data

A participant who withdraws from the study for any reason will be included in the analyses regardless of time on study. Methods for handling withdrawals and missing data will be specific to each endpoint to be analyzed. Missing data will not be imputed for descriptive statistical summaries in safety or efficacy.

For statistical inferential (models) analyses, missing data will be imputed using last observation carried forward (LOCF) method for hemoglobin and other efficacy endpoints. e.g. for primary endpoint, hemoglobin, when Day 35 data is missing (subject has discontinued before Day 35, or measurement not taken at Day 35 though subject was not discontinued), Day 28 result will be carried forward. If the post-baseline value of the first scheduled visit is missing, the worst value obtained from the same time point of all subjects in ITT population will be used for both treatment groups. The worst value is defined as the lowest value for hemoglobin, ferritin, TSAT and reticulocyte hemoglobin content.

Supportive analyses will assess the impact of missing values on inferences based on primary efficacy endpoints and missing data will be handled by using missing at random (MAR) in

mixed effect model repeat measurement (MMRM) model. The observed case will also be applied for primary analysis.

Dates missing the day or both day and month of the year will adhere to the following conventions to classify TEAE and to classify prior/concomitant medications.

- A medication with a completely missing start date will be considered a prior medication. A medication with a completely missing stop date will be considered a concomitant medication.
- If complete AE onset date is missing and AE end date is on or after the first dose date then it will be counted as a treatment emergent AE (TEAE) for the study. If complete AE onset date is missing and AE end date is before the first dose date then it will be counted as a not treatment emergent AE (TEAE) for the study.
- If an AE or a medication has a partial missing start or stop date, the following rules will be used for imputation:
  - If year is present but month and day are missing, impute start date as January 1 of that year or first dose date if the year is the same as the year of first dose date and impute stop date as December 31 of that year.
  - If year and day are present but month is missing, impute start month as January or the month of the first dose date if the year and day is the same as the year and day of first dose date and impute stop month as December.
  - If year and month are present but day is missing, impute start date as first day of that month or first dose date if the year and month are the same as the year and month of first dose date and impute stop date as last day of that month.

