## 6. EFFICACY ANALYSES

All efficacy analyses will be based on the ITT Population. Missing data will be imputed per Section 2.3.4 for statistical inference analysis (no imputation for descriptive statistical summaries).

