### 6.1 PRIMARY EFFICACY ANALYSIS

#### 6.1.1 Change in hemoglobin from baseline to Day 35

The actual value of hemoglobin on baseline, Day 35, and change from baseline to Day 35 will be summarized via descriptive statistics by treatment group.

Treatment group difference for change in hemoglobin will be assessed with the analysis of covariance (ANCOVA), with treatment and randomization strata (hemoglobin and age categories) as fixed factors and baseline value of hemoglobin as a covariate. Baseline hemoglobin will be defined as the last hemoglobin obtained before randomization. Missing value will be imputed using LOCF as specified in Section 2.3.4. P-values to test treatment effect will be determined. Point estimates, associated 95% confidence interval and p-values will be reported.

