#### **MMRM Analysis of Change in hemoglobin from baseline to Day 35:**

A mixed model repeated measures (MMRM) model will be conducted to provide an analysis under the assumption that data are missing at random (MAR). The MMRM model will include changes in hemoglobin from baseline to each post-baseline visit as the dependent variables; and treatment group, visit and treatment group by visit interaction as fixed effects; and subjects within treatment group as random effects; and baseline hemoglobin (<10, ≥10 g/dL) and age (1 to <12 and ≥12 to 17 years) as covariate. An unstructured covariance matrix will be used to allow for unequal variances between visits. If the model does not converge with unstructured variance – covariance matrix, then the Toeplitz, first-order autoregressive, compound symmetric, variance components structures will be tried and the covariance structure will be decided based on model convergence status and the AKaike information criterion. The Kenward-Roger approximation will be used to calculate the denominator of degrees of freedom for the fixed effect. If the interaction term is not significant, it will be dropped from the model. No imputation of missing data other than that inherent in the MMRM model will be performed. P-values to test treatment effect on Day 35 will be reported. Point estimates and associated 95% confidence interval will be reported.

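### The primary ANCOVA fills a missing Day 35 hemoglobin by LOCF, so early dropouts contribute Day 7 or Day 14 values as Day 35 results and can bias the treatment difference in either direction

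*SAP*

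**What the plan says.** SAP 2.3.4 sets the general rule for model-based analyses: "missing data will be imputed using last observation carried forward (LOCF) method for hemoglobin and other efficacy endpoints". It covers both discontinuation before Day 35 and a Day 35 sample that was not taken. Its one worked example says that the "Day 28 result will be carried forward", and it gives no separate rule for someone who left before Day 28. As stated, LOCF then carries Day 14 or Day 7.

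SAP 6.1.1 repeats the rule for the primary ANCOVA: "Missing value will be imputed using LOCF as specified in Section 2.3.4". The same instruction appears for the subgroups (6.1.2), ferritin (6.2.1) and TSAT (6.2.2). SAP section 6 fixes the population: "All efficacy analyses will be based on the ITT Population".

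Two other analyses of the primary endpoint are planned. One is a supportive MMRM under MAR, for which "No imputation of missing data other than that inherent in the MMRM model will be performed". The other is named in 2.3.4: "The observed case will also be applied for primary analysis". Neither replaces the LOCF-based estimate and p-value.

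A different rule, beginning "If the post-baseline value of the first scheduled visit is missing, the worst value obtained from the same time point of all subjects", governs a missing first post-baseline visit. It is outside this point.

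**The concern.** LOCF recovers the Day 35 mean only if hemoglobin is flat after the last visit. At the early visits that is unlikely. FCM is given on Days 0 and 7 and oral iron for 28 days (protocol 5.2). A Day 7 sample comes on the day of the second FCM dose and cannot show its effect. At Day 14 the oral course is half complete. The only Day 35 change on FCM in the documents is large: 2.8 g/dL (SD 1.15) after a single 15 mg/kg dose (protocol Table 1).

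Unequal dropout is plausible. The study is open-label (SAP 1.3.3), and the control is a class of therapy to which these children have already responded inadequately (protocol 4.2.1). At stake is whether the primary estimate is the Day 35 effect, and whether its test keeps its nominal error rate. Filled-in values are also analysed as though they had been measured, so the standard error carries no imputation uncertainty.

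**Working it through.** **The plan's own figure.** Difference 1.0, SD 1.16, two-sided 0.05, 90% power (protocol 8.6): n per arm = 2 × (1.96 + 1.2816)² × 1.16² / 1.0² = 2 × 10.51 × 1.3456 = 28.3, so 29. With the t distribution, power is 89.7% at 29 and 90.7% at 30, so 30 per arm is reproduced. With 36 per arm and no missing data it is 95.0%.

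**Inputs from the documents.** 72 randomized 1:1 (36 per arm); SD 1.16; visits at Days 7, 14, 28 and 35; FCM gain of 2.8 g/dL from the Phase II study, which with the planned difference of 1.0 implies 1.8 on oral iron.

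**Inputs assumed.** Dropout by arm; last visit equally often Day 7, 14 or 28; shape of the rise. Two shapes are used, as shares of the Day 35 gain reached at Days 7/14/28/35: linear (20/40/80/100%) and saturating (43/69/94/100%).

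**Formula.** Let d be the share of an arm imputed and g the rise still to come after the last visit. The bias in FCM minus oral is d(oral) × g(oral) − d(FCM) × g(FCM), where g = Day 35 gain × r. The mean remaining share r is:
- linear: (0.80 + 0.60 + 0.20)/3 = 0.533
- saturating: (0.57 + 0.31 + 0.06)/3 = 0.313

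**Bias, saturating to linear.**

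| Scenario (dropout FCM / oral) | Before multiplying by r | Bias, g/dL |
|---|---|---|
| A. No effect, gain 1.8, 5% / 20% | 0.20×1.8 − 0.05×1.8 = 0.27 | +0.085 to +0.144 |
| B. As A, gain 0.5 | 0.15×0.5 = 0.075 | +0.02 to +0.04 |
| C. As A, only Day 28 carried (r = 0.06 or 0.20) | 0.27 | +0.02 to +0.05 |
| D. Gains 2.8 v 1.8, 20% / 5% | 0.05×1.8 − 0.20×2.8 = −0.47 | −0.15 to −0.25 |
| E. Gains 2.8 v 1.8, 20% / 20% | 0.20×1.8 − 0.20×2.8 = −0.20 | −0.06 to −0.11 |

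Cancellation is possible. With gains of 2.8 and 1.8, the same timing and 20% oral dropout, the bias is zero at FCM dropout of 0.20 × 1.8 / 2.8 = 12.9%.

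**Rejection rates.** Simulation with 36 per arm, visit SDs 0.6/0.85/1.10/1.16, correlation 0.8 per week, dropout unrelated to outcome, unadjusted two-sample t-test, 8,000 trials per scenario:
- A: bias about +0.09 to +0.14; FCM-favouring rejections about 5–7% (nominal 2.5%).
- B and C: about 3–4%.
- D: LOCF power about 71–85%, against about 91% for observed Day 35 values only.
- E: LOCF power about 85–92%, against about 89% for observed values only.

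The bias formula does not depend on the test. The rejection rates do, and the planned ANCOVA was not simulated.

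**The case against.** The strongest reply is that the damage is hypothetical and partly covered. Dropout by arm and its timing are assumptions; the 20% in protocol 8.6 concerns failure to meet the mITT definition, not a missing Day 35 value. The SAP's only example carries Day 28, where little rise may remain. A 1.8 g/dL gain on oral iron sits awkwardly with children who have already responded poorly to it. The protocol also limits missing data: participants who stop drug may stay on the visit schedule (4.5), those with concomitant interventions continue (4.6), and Day 35 procedures are done at exit (6.3.4). The MMRM and observed-case analyses would show a material distortion.

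Most of this stands as a limit on size: scenarios B and C are near nominal. It does not rescue the rule. The supportive analyses do not replace the primary result, and the SAP does not say which prevails if they disagree. The exit visit cuts both ways: with no analysis windows (SAP 2.3.3), an early-termination sample could be labelled Day 35, which creates the same problem without LOCF.

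Three stronger readings are tempting and not supported:
- *Any difference in dropout biases the result, in favour of FCM.* Unequal dropout can cancel, equal dropout can bias, and the sign depends on the arm.
- *LOCF costs power in general.* The 95% figure assumes no missing data. The fair benchmark is observed case, and with equal dropout LOCF can exceed it (92% against 89%, saturating).
- *The planned MMRM can simply be promoted.* As written it drops a non-significant treatment-by-visit interaction, which leaves one effect common to all visits, and it lists baseline hemoglobin only as <10/≥10.

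**Conclusion.** The point holds. LOCF is the primary missing-data rule, and for participants last seen at Day 7 or 14 it substitutes a mid-study value for the Day 35 outcome. The resulting bias is zero only if dropout share times remaining rise happens to balance between arms.

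A continuing rise at Days 7 and 14 is a well-founded inference from the dosing periods. A rise from Day 28 to 35 is not shown, and bias from carrying Day 28 is small or nil. The scenario figures illustrate the mechanism and do not predict this trial: they rest on assumed dropout, timing, curve shape and oral gain. A power loss should be claimed only for excess FCM dropout, or for equal dropout with a near-linear rise. This should be changed before database lock; it does not by itself invalidate the trial.

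**What to change.** - Keep the SAP 6.1.1 ANCOVA on the ITT population. Replace LOCF with multiple imputation under MAR, done separately by arm, using hemoglobin at all visits, the baseline value and the randomization strata, and combined by Rubin's rules.
- Move LOCF to a sensitivity analysis. Make the same change for ferritin and TSAT.
- If the MMRM Day 35 contrast is made primary instead, always keep the treatment-by-visit interaction and use continuous baseline hemoglobin.
- State that early-termination samples (protocol 6.3.4) are analysed at their actual time and not labelled Day 35.

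The cost is SAP wording and a few lines of code before lock, with no new data, visits or sample size. The confidence interval will be slightly wider because it then carries imputation uncertainty.

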### 6.3 Treatment Phase (Day 0 to Day 35)

#### 6.3.1 Day 0 Visit

The following will be obtained and/or completed before contacting IRT for randomization:

For all participants:

- Verify all inclusion and exclusion criteria (See section 4.2.1 and 4.2.2)
- Physical exam
- Review concomitant medications (to include ESA and IBD stability, if applicable).

A participant who develops a bacterial infection during the screening phase should be discontinued and treated appropriately. These participants may be re-screened, one time, once the enrolling physician deems the participant would qualify for study entry. The participant will need to re-sign a new consent / assent form and all screening procedures in section 6.2 will need to be repeated.

After verifying the eligibility of the participant, the IRT system will then be contacted by a study team member. Randomization will be stratified by hemoglobin (<10, ≥10 g/dL) and age (1 to <12 and ≥12 to 17 years), and randomized in a 1:1 ratio to either Group A (FCM at 15 mg/kg to a maximum single dose of 750 mg on Days 0 and 7 for a maximum total dose of 1500 mg) or Group B (Ferrous sulfate, dose and regimen dependent upon age and weight, twice daily for 28 days).

After a randomization number has been obtained, the **first dose** of oral ferrous sulfate will be administered in the clinic according to the following: infants and children (1 to <4 years of age) will receive ferrous sulfate drops; children (≥4 to <12 years of age) will receive ferrous sulfate elixir or ferrous sulfate tablets; and adolescents (≥12 to 17 years of age) will receive ferrous sulfate tablets.

A sufficient quantity of doses for a 7-day period will be dispensed to the parent or guardian of the participant. The parent or guardian of the participant will be responsible for the administration of two daily doses of oral ferrous sulfate to the participant.

After assignment of the treatment group, the following will occur:

All participant's (prior to study drug administration/dispensing, if applicable) on Day 0:

- Blood samples for central lab hematology, chemistries, and iron indices (Group

- A participants will have an additional blood sample for PK prior to dosing)
- Vital signs: temperature, sitting heart rate and blood pressure
- Weight

Group A:

- Blood samples for PK immediately (within 5 minutes) post-dose and 60 minutes post dose.
- Verify amount of single FCM dose (15mg/kg up to a maximum single dose of 750 mg).

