### 1.3 SUMMARY OF THE STUDY DESIGN

#### 1.3.1 General Study Design and Plan

This is a Phase III, multicenter, multinational, randomized, active-controlled study that compares the efficacy and safety of FCM to oral iron in pediatric participants with IDA and a documented history of an inadequate response to oral iron therapy at least 8 weeks (56 days) prior to screening.

FCM injection is a stable, non-dextran, Type I polynuclear iron (III) -hydroxide carbohydrate complex developed as an intravenous (IV) iron replacement therapy for the treatment of IDA. The duration of this study is approximately 6 weeks and the number of sites is approximately 30. Participants who satisfy the inclusion requirements and no exclusion criteria will be eligible to participate in this study and enter into a screening phase to confirm eligibility. All eligible participants will be randomized in a 1:1 ratio to receive either FCM at 15 mg/kg to a maximum single dose of 750 mg on Days 0 and 7 for a maximum total dose of 1500 mg in Group A or oral iron (oral solution drops, elixir or oral tablets) twice daily for 28 days in Group B. Randomization will be stratified by baseline hemoglobin (<10,  $\geq$ 10 g/dL) and age (1 to <12 and  $\geq$ 12 to 17 years). The oral ferrous sulfate formulation received will be based on the participant's age, such that infants and children (1 to <4 years of age) will receive ferrous sulfate drops, children ( $\geq$ 4 to <12 years of age) will have the option to receive ferrous sulfate elixir or ferrous sulfate tablets, and adolescents ( $\geq$ 12 to 17 years of age) will receive ferrous sulfate tablets. If the participants experience adverse clinical symptoms due to the oral iron during the treatment phase, the weight-based dose of ferrous sulfate will be reduced from 6 mg/kg to 3 mg/kg. As for the participants who receive tablets, the dose will be reduced from one tablet taken twice daily to one tablet per day.

Once randomized, all participants will return for efficacy and safety evaluations, including adverse events and laboratory assessments, on Days 7, 14, 28, and 35. Additional pharmacokinetic sampling and analyses will be performed for participants receiving FCM on Days 0 and 7.

The Schedule of Events is presented by Table 1.

Table 1 Schedule of Events

Visit Day	Screening (Day -7 + 1)	Day 0	Day 7	Day 14	Day 28	DAY 35
Informed Consent / Assent	X					
Medical History	X					
Physical Exam		X				X
Inclusion/Exclusion Criteria	X	X				

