## 2.2 DEFINITIONS OF ANALYSIS POPULATIONS (ANALYSIS SETS)

### 2.2.1 Intent-to-Treat Population

The Intent-to-Treat (ITT) population will comprise all randomized participants. Participants will be evaluated according to the treatment to which they were randomized. Any participant who receives a treatment randomization number will be considered to have been randomized. Unless otherwise stated, disposition and baseline data will be summarized in ITT population. The primary population for assessing efficacy will be the ITT population.

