## 2.3 DEFINITIONS AND CONVENTIONS FOR DATA HANDLING

### 2.3.1 Baseline Definition

For evaluations collected at multiple time points, the baseline will be defined as the last value obtained before randomization.

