## 9. SUMMARY OF MAJOR CHANGES IN THE PLANNED ANALYSES

Compared with the study protocol (26SEP2019 Administrative Change 1), below items are the major changes made in this SAP:

1. The efficacy analyses will be conducted for the ITT population instead of the mITT population to be more in keeping with accepted practice. The mITT population will still be defined and will be used for post-hoc sensitivity analyses.
2. In protocol, the sentence of “Changes from baseline in hemoglobin, ferritin, TSAT, and reticulocyte hemoglobin content throughout the study” in [section 8.4.2](#) is not consistent with the sentence in study synopsis. In this SAP, we just keep this endpoint in consistency with descriptions in synopsis.
3. To assess the robustness of primary and secondary efficacy analysis, supportive analyses will be performed using MMRM model.
4. The scale defined in Division of AIDS (DAIDS) Table for Grading the Severity of Adult and Pediatric Adverse Events, Version 2.1 from March 2017 (Division of AIDS, National Institute of

Allergy and Infectious Diseases, National Institutes of Health, US Department of Health and Human Services) will be used to identify abnormal clinical laboratory values instead of toxicity criteria from the National Cancer Institute Common Terminology Criteria version 5 for Adverse Events specified in the protocol.

5. The subgroups Cause of IDA: IBD, not IBD and CKD, not CKD are not included in this SAP because of insufficient sample size for meaningful estimates.

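### In the primary ITT analysis, SAP 2.3.4 would most naturally give a randomized child with no post-baseline hemoglobin the lowest Day 7 value of any child, and the visit is not named

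*SAP*

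**What the plan says.** SAP 2.3.4 uses last observation carried forward (LOCF) for inferential analyses. If the value at the first scheduled post-baseline visit is missing, it adds that "the worst value obtained from the same time point of all subjects in ITT population will be used for both treatment groups", and defines worst as lowest for hemoglobin, ferritin, TSAT and reticulocyte hemoglobin content.

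SAP 6.1.1 brings this into the primary ANCOVA: "Missing value will be imputed using LOCF as specified in Section 2.3.4". The analysis set is all randomized children: "The primary population for assessing efficacy will be the ITT population". SAP section 9 records this as a change from the protocol: "The efficacy analyses will be conducted for the ITT population instead of the mITT population". The protocol's mITT set (8.2) required a dose, a baseline hemoglobin and at least one post-baseline value.

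On timing, SAP 1.3.1 says "all participants will return for efficacy and safety evaluations, including adverse events and laboratory assessments, on Days 7, 14, 28, and 35". SAP 2.3.1 says "the baseline will be defined as the last value obtained before randomization". Protocol 6.3.1 lists the Day 0 central-laboratory sample, taken before dosing, under the line "After assignment of the treatment group, the following will occur".

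The supportive analyses are an observed-case analysis and an MMRM, for which SAP 6.1.1 states "No imputation of missing data other than that inherent in the MMRM model will be performed".

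**The concern.** The imputed value is an absolute hemoglobin from the worst child in the trial. It takes no account of the affected child's own baseline, stratum or arm. The endpoint is a change from baseline, so each such child enters the ANCOVA as a large fall in a trial where both arms are expected to rise. A few such values inflate the residual variance and cost power. If the arms lose different numbers of children, the treatment estimate shifts against the arm that loses more.

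The mITT set would have left these children out, and the ITT set brings them in. The first visit and the donor time point are also unnamed, so two programmers could obtain different primary results from the same data.

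**Working it through.** **1. The plan's own figure.** Protocol 8.6 and SAP 1.3.4 give a difference of 1.0 g/dL, SD 1.16, two-sided alpha 0.05 and 90% power. Per arm, n = 2(z₀.₉₇₅ + z₀.₉₀)²σ²/δ² = 2 × (1.960 + 1.282)² × 1.16² / 1.0² = 28.3, so 29. The noncentral t gives 89.7% power at 29 and 90.7% at 30, so 30 per arm is confirmed. With 36 per arm and no loss, the simulated SAP ANCOVA has about 94% power.

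**2. Who is affected.** A child who misses Day 7 but has a hemoglobin on Day 14, 28 or 35 is covered by the observed value or ordinary LOCF. The rule reaches the primary endpoint only for a randomized child with no post-baseline hemoglobin at all.

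**3. How many.** Protocol 8.6 assumes 20% attrition for not meeting the mITT definition and goes from 60 to 72. That leaves room for 72 - 60 = 12 children, or 6 per arm if equal. This group largely overlaps the affected children. SAP 1.3.4 keeps 72 but drops the percentage.

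**4. Readings of the rule.**
- Day 7 donor: the first return visit in SAP 1.3.1, and the natural reading.
- Day 35 donor: possible, because Day 35 is the value being imputed.
- Day 0: literally possible, because the sample is listed after assignment and baseline is the last value before randomization. The child's own pre-dose value would then be carried forward. This reading is weaker, because Day 0 is not among the return visits.

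**5. Simulation inputs.** From the documents: 36 per arm, difference 1.0, SD 1.16, the two Phase II screening distributions in Protocol 3.2 Table 1 (9.2, SD 1.20; 9.5, SD 0.81), truncated below 11 by the entry criterion. Assumed: number lost, oral change 0.8 at Day 35, Day 7 mean change 0.4 (FCM) and 0.3 (oral), Day 7 SD 0.6, Day 7/Day 35 correlation 0.5. The model is the SAP ANCOVA: treatment, two strata and continuous baseline. The ranges below cover both baselines and repeat runs.

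**6. Results, Day 7 donor.** The imputed change is about -2.0 to -2.7 g/dL.

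| Lost per arm (balanced), true difference 1.0 | Power, SAP rule |
|---|---|
| 0 | about 94% |
| 1 | 88-90% |
| 2 | 79-86% |
| 3 | 68-78% |
| 6 | 41-56% |

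Observed-case power is about 87-93% over the same losses.

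| Lost, FCM vs oral, no true difference | Type I error, SAP rule |
|---|---|
| 2 vs 2 | about 2% |
| 0 vs 2 | 6-8% |
| 0 vs 3 | 9-12% |
| 0 vs 4 | 13-17% |

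**7. Hand check.** A separate run used baseline mean 9.5 and SD 1.0, 20% of the Day 35 change reached by Day 7, and Day 7 noise SD 0.5.
- Bias, three oral children lost, no true effect: 3/36 × (0.8 + 2.36) = +0.26 g/dL; simulated +0.27.
- Three FCM children lost, true difference 1.0: 1.0 - 3/36 × (1.8 + 2.32) = 0.66; simulated 0.65, power 47%.
- Six lost per arm: the estimate shrinks to 30/36 × 1.0 = 0.83; simulated 0.83. The gaps between observed and imputed mean change are 1.8 + 2.27 = 4.07 (FCM) and 0.8 + 2.27 = 3.07 (oral), with mean square 13.0. Residual SD is about √(30/36 × 1.16² + 30/36 × 6/36 × 13.0) = √(1.12 + 1.81) = 1.71. The simulation gives 1.76; the remainder comes from spread among the imputed changes.

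**8. Other readings.** In that separate run, the Day 35 donor gives 82% power at two per arm and 48% at six, against 81% and 47% for Day 7. On the Day 0 reading (assumed screening-to-Day 0 noise SD 0.4), power is about 92% at two per arm and 90% at three, and type I error at 0 vs 4 is 6-7%. The harm nearly disappears.

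**The case against.** The rule is prespecified and gives the same value to both arms. With balanced loss it is conservative for type I error. It touches only children with no later hemoglobin, and with one such child per arm power is still about the 90% design target. Protocol 6.3.4 asks for the Day 35 procedures before a child leaves the trial, and Protocol 4.5 asks children who stop study drug to keep to the schedule, so the number may be small. MMRM and observed-case analyses are already planned. The sentence may be generic: it names reticulocyte hemoglobin content, for which SAP 6.2.6 has no imputed analysis. Missing at random is itself a strong assumption in an open-label trial.

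All of this limits the size of the concern. It does not remove it. The rule is conservative only when loss is balanced. The supportive analyses would reveal a discrepancy but are not the primary test.

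Four stronger readings go further than the documents allow:
- A reader might infer that every child who misses Day 7 is penalized. A later observed value takes precedence.
- A reader might infer that the rule favours FCM. It does so only if more oral-arm children lack follow-up; the reverse imbalance works against FCM, and the documents predict neither.
- A reader might take the 12 children as a forecast. The figure is a planning allowance, and some could fail mITT for other reasons.
- A reader might treat the Day 7 donor and the carry-forward to Day 35 as stated. Both are the natural reading, but neither is written out.

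**Conclusion.** The point holds and should be fixed. The text defect does not depend on any simulation: a stated rule feeds the primary ITT analysis, assigns a value unrelated to the child, and names neither the visit nor the donor time point.

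The size is conditional. It needs the Day 7 or Day 35 reading, plus either about two affected children per arm (power 79-86%) or an excess of about three in one arm (type I error 9-12% if the loss is in the oral arm). At the full planning allowance of six per arm, power would be 41-56%. These figures rest on the assumed oral response, Day 7 behaviour and loss counts, with loss unrelated to outcome.

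**What to change.** Before database lock, until which SAP 1.3.3 keeps the study statisticians blinded to assignment:

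1. Remove the worst-value sentence from the primary analysis.
2. For randomized children with no post-baseline hemoglobin, use multiple imputation of the Day 35 change under missing at random, from arm, both strata and continuous baseline hemoglobin. In a check with 20 imputations, power was 92-93% at two lost per arm, and at 0 vs 4 with no effect type I error was 4-5% with bias within 0.003 g/dL. This adds no information over observed case; it keeps the ITT set complete.
3. Do not promote the MMRM in SAP 6.1.1 as written. It drops a non-significant treatment-by-visit interaction, so the Day 35 effect could become an average over all visits. It uses baseline hemoglobin only as a category. A child with no post-baseline value contributes no outcome to it.
4. Keep the worst-value rule, or a reference-based imputation, as a sensitivity analysis for informative loss, and name its donor time point.
5. State that the first post-baseline visit is Day 7 and that the pre-dose Day 0 sample is not a post-baseline value.

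The cost is SAP wording and some programming, with no new data or participants. The downside is a missing-at-random assumption for these children. The method was not tested under missing not at random, which is why step 4 is needed.
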